## 5. EARLY DISCONTINUATION OF PARTICIPANTS

### 5.1 Withdrawal from study

Withdrawal from the study, which is different to withdrawal from QOL, refers to discontinuation of study follow-up and can occur for the following reasons:

- Participant decision
- Loss to follow-up – where patient has been contacted multiple times during the follow-up over a period of time and unable to get in touch with them and/or hasn't been attending any appointments

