## **4.7 Follow Up**

Follow up at all UK centres will be conducted by a central trial hub utilising:

1. Online questionnaires and/or telephone contact with the participant or their nominated representative completing questions onto the OpenClinica ePRO database. This will occur every 6 months starting from device implantation.
2. Remote follow-up from a participant's pacemaker where available, downloads will be scheduled every 6 months. Where possible data will be transferred from device companies to the trial team either directly or via the implanting/recruiting centre.
3. For participants residing in England – mortality and hospital statistics will be obtained by data draws every 24 months from nationally held records.

PROTECTHF	Protocol No: 22HH7931	Sponsor: Imperial College London	V9.0 16-Jun- 2025
------------------	--------------------------	-------------------------------------	----------------------

Additionally, the central staff will contact participants if made aware by local study team or by the participant of an adverse events and will follow this up accordingly.

Incidental findings identified as part of the research protocol will be reviewed and reported by the clinical members of the research team. Any incidental findings identified will be communicated to the patient's clinical team as well as their GP as per standard protocol.

In some international centres, patients will be contacted by their local site teams instead of the central trial hub. Some international centres may conduct streamlined follow-up, collecting data on HFH and mortality only. Some international centres may also conduct 1-yearly follow-up instead of 6-monthly follow-up and this may be based on data from a national registry instead of via telephone calls to participants directly.

Participants can withdraw from questionnaire and where this is noted, the applicable participants will be followed up on their medical records only, if participants consents to this. A protocol deviation should be raised where participants want to withdraw from questionnaires.

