### 5.3 Procedures for permanent discontinuation or withdrawal from the trial

- If a participant permanently discontinues the trial intervention, they will be invited to continue to attend trial visits if possible to allow for collection of key outcome and safety data.
- If the participant withdraws consent to further be contacted at all for the study purposes, this will be documented on the electronic case report form (eCRF) and in the medical notes. No attempts of further contact will be made.
- Participants who have discontinued the trial intervention and/or have withdrawn from the trial will not be replaced.

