Some people with capacity will consent to take part in research, but then may lose capacity before the end of the study. We will assume capacity is present unless established otherwise; should concerns arise, members of our clinical team will take steps to assess capacity status. If we become aware that a participant has lost capacity prior to implant they will be withdrawn from the study at this time-point. If a participant has lost capacity after implant there are no risks involved in the follow-up as both arms are receiving guideline indicated therapies. Primary endpoint data will be collected via their healthcare records and when necessary liaising with local research and clinical teams. For participants who lose capacity and are consented to the echo sub-study, they will not have their echocardiograms, if they have yet to have one or both. The participant and nominated other will not be contacted in any way or for any reason to obtain information required for endpoint data, this includes stopping the 6-monthly telephone follow-up visits.

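### Section 5.1 treats losing contact as withdrawal and so ends study follow-up, although primary events could still be collected from records

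*Protocol*

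**What the plan says.** Section 5.1 states that withdrawal from the study "refers to discontinuation of study follow-up and can occur for the following reasons". Two reasons follow. One is the participant's decision. The other begins "Loss to follow-up – where patient has been contacted multiple times during the follow-up" and also covers not attending appointments. The same section sets this apart from giving up the quality-of-life questionnaires only.

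Section 5.3 gives a procedure for two situations. A participant who stops the trial intervention stays in view: "they will be invited to continue to attend trial visits if possible to allow for collection of key outcome and safety data". The other situation opens "If the participant withdraws consent to further be contacted at all for the study purposes" and ends all contact. A participant who cannot be reached but has not withdrawn consent falls under neither.

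Elsewhere the protocol collects endpoints without contact:
- Section 4.7, after questionnaire withdrawal: "the applicable participants will be followed up on their medical records only, if participants consents to this".
- Section 8.8, after loss of capacity following implant: "Primary endpoint data will be collected via their healthcare records and when necessary liaising with local research and clinical teams".
- Sections 4.7 and 4.9: national data draws every two years for participants living in England, to the formal end of the trial.
- Section 4.7: a national registry in place of telephone calls at some international centres.

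**The concern.** Being unreachable is not a refusal, and section 5.1 itself lists it apart from the participant's decision. The primary endpoint (death, unplanned heart failure admission or ambulatory diuretic therapy) can be sought in hospital records without speaking to anyone. As worded, a participant who stops responding may have less endpoint information collected than one who has lost capacity and is no longer contacted at all.

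The primary analysis (section 7.3) is intention to treat with Kaplan-Meier, log-rank and Cox methods, so these participants would ordinarily be censored at last contact. In a pacemaker population, silence can follow admission, frailty or death, so censoring may be related to the outcome. An analysis plan cannot restore data that the protocol tells staff to stop collecting, and the 7% drop-out allowance in section 7.1 protects power but does not correct bias.

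**Working it through.** **1. The texts side by side**

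| Participant | Consent | Endpoint collection stated |
|---|---|---|
| Stops questionnaires (4.7) | Stands | Medical records, if the participant consents |
| Loses capacity after implant (8.8) | Given earlier | Healthcare records and local teams, no contact |
| Stops the intervention (5.3) | Stands | Invited to continue trial visits |
| Cannot be contacted (5.1) | Not withdrawn | Study follow-up discontinued |

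Section 4.7 lists the England draws as part of follow-up, which 5.1 ends. Section 4.9 continues them to the end of the trial with no exception. The two are not reconciled.

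**2. The plan's own figure**

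Inputs from sections 4.3, 7.1 and 7.2: control survival 0.725 at 4 years, HR 0.78, 85% power, two-sided 5%, 3.5 years of recruitment plus 3 years of follow-up, 1:1 allocation, 2600 participants.
- Control hazard h = −ln(0.725)/4 = 0.0804 per year; physiological arm 0.78 × 0.0804 = 0.0627.
- Event probability with uniform entry: p = 1 − [exp(−3h) − exp(−6.5h)]/(3.5h) = 0.3152 (control) and 0.2561 (physiological), mean 0.2856.
- Events needed (Schoenfeld): 4 × (1.960 + 1.036)²/(ln 0.78)² = 582. N = 582/0.2856 = 2038. Freedman's formula gives 588 events and N = 2059. The stated 2048 is reproduced.
- Expected events at 2600: 1300 × (0.3152 + 0.2561) = 743.

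**3. Events that would go unseen**

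Assumed model: a proportion L of an arm is lost, at a uniformly distributed time before the event or the end of follow-up. Participants who have an event are k times as likely to be lost. Then q = L/(1 − p + kp) is the loss probability without an event, and hidden events per arm = 1300 × p × k × q. L = 7% is the planned drop-out (182 of 2600); k is my assumption.
- k = 1: 1300 × 0.07 × (0.3152 + 0.2561) = 52.
- k = 2: q = 0.07/1.3152 = 0.0532 and 0.07/1.2561 = 0.0557. Hidden = 1300 × (0.3152 × 0.1065 + 0.2561 × 0.1115) = 43.6 + 37.1 = 81.

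If all England losses are recovered (about 1500 of 2600, section 7.3 item v), multiply by 1 − 1500/2600 = 0.423. This leaves 22 to 34.

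**4. Effect on the hazard ratio**

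I approximate the HR by the ratio of events per person-year, with no crossover dilution. Observed rate = p(1 − kq)/[E(1 − kq/2) + F(1 − q/2)]. Here E and F are the mean person-years from participants with and without an event: 0.723 and 3.197 (control), 0.598 and 3.486 (physiological). Lost participants contribute half their time on average.

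| Loss RV / physiological | k | HR, none recovered | HR, England recovered |
|---|---|---|---|
| 7% / 7% | 1 | 0.780 | 0.780 |
| 7% / 7% | 2 | 0.776 | 0.778 |
| 9% / 5% | 2 | 0.0591/0.0723 = 0.817 | 0.794 |
| 5% / 9% | 2 | 0.0560/0.0760 = 0.737 | 0.763 |

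The last column replaces q by 0.423q. Simulating the same model gives 0.81 to 0.82 and 0.73 to 0.74 with no recovery.

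One caution about k = 1. Loss in this model always precedes the event, so equal loss probabilities are already mildly outcome-related. A 9%/5% split with k = 1 gives 0.78 × (0.95/0.975)/(0.91/0.955) = 0.798, and 0.763 reversed. Under truly independent censoring an unequal split would leave 0.78 unchanged.

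**5. Power**

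With 7.5% crossover the HR dilutes to 0.925 × 0.78 + 0.075 = 0.7965. At 2600 participants, power is 87.6% with no loss (749 events) and 86.2% with 7% lost by 4 years (718 events). Power is not the problem.

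**The case against.** A reader might infer that all primary events in these participants are lost. The protocol does not support that. Section 4.9 continues the England draws with no exception for lost participants, and 4.10 uses them to confirm mortality and hospital events. Contact may be with a nominated representative, local teams report deaths and heart failure events as adverse events (6.4), routine pacing checks continue at sites, and some international centres may use a registry. This limits the harm. It leaves about 2600 − 1500 = 1100 participants for whom no route is assured once they are classed as withdrawn. Nor does the protocol say whether the draws capture diuretic lounge visits.

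A reader might also infer that section 5.3 abandons participants who stop the intervention. It does not: it keeps them in follow-up for outcome data. Its only gap is that it speaks of visits and not of records.

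A third tempting inference is that the hazard ratio will be biased. No loss rate by arm or by outcome is given. Patients are blinded and UK follow-up is run centrally, so a reason for unequal loss is conjecture. The 7% also includes participants who decide to leave, and some of those may refuse use of their records.

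Finally, 4.7 makes records-only follow-up conditional on consent, and an unreachable person cannot give fresh consent. That stands as a limit on the fix.

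**Conclusion.** The wording fault is clear. Section 5.1 turns loss of contact into an end of follow-up, against the protocol's own practice in 4.7 and 8.8, and leaves 4.9 unreconciled. The consequence is a risk, not a demonstrated bias. It falls mainly on the roughly 1100 participants outside England.

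Its size is bounded by treating the whole 7% drop-out as uncontactable: about 52 to 81 of 743 events unseen with no recovery, and 22 to 34 with full England recovery. Equal loss leaves the HR within about 0.004 of 0.78 for k up to 2. A material shift needs loss that is both outcome-related and unequal by arm: to about 0.81–0.82 or 0.74 under the assumed 9%/5% split and twofold link, shrinking to about 0.79 or 0.76–0.77 with England recovery. The direction depends on which arm loses more. The split, the link and complete England recovery are assumptions, not figures from the protocol. The change should be made because the collection routes already exist and it is cheap.

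**What to change.** - In 5.1, delete loss to follow-up from the reasons for withdrawal.
- State that participants who cannot be contacted and have not withdrawn consent remain in record-based follow-up for death, heart failure admission and ambulatory diuretic therapy, to the common end date and within the scope of their existing consent. Sources: site records and local teams, NHS digital in England, a national registry where used.
- Record the level of withdrawal in the eCRF: no questionnaires; no contact but records; no further data.
- Reconcile 5.1 with 4.7, 4.9 and 8.8, saying explicitly whether the England draws continue for participants who cannot be reached.
- In 5.3, add only that record-based endpoint collection continues after the intervention is discontinued.

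The cost is a protocol amendment, one eCRF field, occasional record look-ups by sites, and a check that the existing consent covers them. The consent form is not among the documents seen, so that check is needed before the wording is settled.

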### 5.2 Permanent discontinuation of trial intervention

Participants may discontinue trial intervention for the following reasons:

- At the request of the participant
- Due to an Adverse Event / Serious Adverse Event
- If the investigator considers that a participant's health will be compromised due to adverse events or concomitant illness that develop after entering the trial.

### 5.3 Procedures for permanent discontinuation or withdrawal from the trial

- If a participant permanently discontinues the trial intervention, they will be invited to continue to attend trial visits if possible to allow for collection of key outcome and safety data.
- If the participant withdraws consent to further be contacted at all for the study purposes, this will be documented on the electronic case report form (eCRF) and in the medical notes. No attempts of further contact will be made.
- Participants who have discontinued the trial intervention and/or have withdrawn from the trial will not be replaced.

## 6. SAFETY REPORTING

### 6.1 Adverse Event (AE)

An AE is any untoward medical occurrence in a patient or clinical trial subject. An AE can therefore be any unfavourable and unintended sign (including an abnormal laboratory finding), symptom, whether or not considered related to the trial protocol.

### 6.2 Causality

Definitions for assessment of causality:

Unrelated:	No evidence of any causal relationship
Unlikely:	There is little evidence to suggest there is a causal relationship (e.g. the event did not occur within a reasonable time after device implantation. There is another reasonable explanation for the event (e.g. the patient's clinical condition, other concomitant treatment).
Possible:	There is some evidence to suggest a causal relationship. However, the influence of other factors may have contributed to the event (e.g. the patient's clinical condition, other concomitant treatments).
Probable:	There is evidence to suggest a causal relationship and the influence of other factors is unlikely.
Definite:	There is clear evidence to suggest a causal relationship and other possible contributing factors can be ruled out.

### 6.3 Severity of Adverse Events

*Definitions for assessment of severity:*

Mild:	Awareness of event but easily tolerated
Moderate:	Discomfort enough to cause some interference with usual activity
Severe:	Inability to carry out usual activity

### 6.4 Adverse Event recording

For the purposes of this trial, only adverse events related to the study, defined medically important events and cardiac events and conditions after consent has been obtained will be recorded and reported on the database. Please see the complete list below of adverse events that must be reported. All related and unexpected serious adverse events must be reported as stipulated in the Safety Reporting instructions, regardless of whether they are in the list of defined reportable adverse events. Expected AEs in this population of patients with Heart Failure will include hospitalisations related to arrhythmia, worsening shortness of breath and chest pain. Other expected events include those that are related to known complications of pacemaker insertion. This includes, but is not limited to, lead displacement +/- revision, wound or device infection, pneumothorax, haematoma and deep vein thrombosis. For the purposes of this trial, AEs, both serious and non-serious, as described above, will be followed up according to local practice until the event has stabilised or resolved, or the Follow-up Visit, whichever is the sooner. *This may require the central team to contact local teams, to provide further information from the participant medical records, regarding an adverse event.*

All other adverse events, both serious and non-serious will not be reported and recorded on the study database; however, they must still be documented in the medical notes and followed up as per local practice by clinical teams. They will not be monitored for the purpose of this study.

Adverse Events that must be reported are:

- Heart Failure Hospitalisation (HFH)
- Ambulatory Heart Failure events (e.g., Ambulatory diuretic therapy)
- Suspected Heart Failure Hospitalisation (HFH)
- Device issues:
  - Device infection (requiring device extraction)
  - Device infection (requiring antibiotics, with or without device extraction)
  - Significant rise in pacing thresholds
  - Lead displacement or perforation
  - Lead revision or reimplantation
  - Generator change
  - Haematoma
  - Pneumothorax
  - Inappropriate pacing function
- Device upgrade
- Major bleeding or haemorrhage related to device implant
- Any cardiac related hospital admission
- Any cardiac related events, including but not limited to:
  - Myocardial Infarction
  - Arrhythmia events
    - Atrial Fibrillation
    - Ventricular Arrhythmia
  - EF changes
    - EF drop to  $\leq 35\%$  OR
    - EF drop to  $\geq 10\%$  drop from baseline
  - Shortness of breath
  - Worsening peripheral oedema
  - Lung atelectasis
  - Pericardial effusion
  - Pleural effusion
  - Chest Pain
  - Changes in cardiac blood markers (BNP, Troponin)
- Any cardiac related Accident & Emergency visit, day-case admission, or unplanned outpatient event or procedure
- Loss of capacity
- Delirium
- Dementia
- Stroke
- Non cardiac death
- Sudden cardiac death (Ventricular Tachycardia / Ventricular Fibrillation arrest)
- Cardiac death

## 6.5 Serious Adverse Events (SAE)

**(i) Definition of SAE**

An SAE is defined as any event that

- Results in death;
- Is life-threatening\*;
- Requires hospitalisation or prolongation of existing inpatient's hospitalisation\*\*;
- Results in persistent or significant disability or incapacity;
- Is a congenital abnormality or birth defect;

\* “Life-threatening” in the definition of “serious” refers to an event in which the participant was at risk of death at the time of the event; it does not refer to an event which hypothetically might have caused death if it were more severe.

\*\* “Hospitalisation” means any unexpected admission to a hospital department. It does not usually apply to scheduled admissions that were planned before study inclusion or visits to casualty (without admission).

Medical judgement should be exercised in deciding whether an adverse event/reaction is serious in other situations. Important adverse events/reactions that are not immediately life-threatening, or do not result in death or hospitalisation but may jeopardise a subject or may require intervention to prevent one of the other outcomes listed in the definition above should also be considered serious.

**(ii) Reporting of SAEs**

Reporting of all SAEs, occurring during the study must be performed as detailed in the study-specific Safety reporting instructions.

Active monitoring of participants after the end of the trial is not required.

All SAEs will be reviewed by the Chief Investigator or a designated medically qualified representative to confirm expectedness and causality.

Expected AEs in this population of patients with Heart Failure will include hospitalisations related to arrhythmia, worsening shortness of breath and chest pain.

Reporting of SAEs and review by the CI will be via the trial data collection system (OpenClinica).

**(iii) Related SAEs**

Related: resulted from administration of any of the research procedures

**(iv) Unexpected SAEs**

Unexpected: type of event is not listed in the protocol as an expected occurrence

**(v) Reporting of SAEs that are related and unexpected**

SAEs that are *related and unexpected* should be notified to the relevant REC and the Sponsor in accordance with local requirements. For Imperial-Sponsored studies related and unexpected SAEs must be reported to the Sponsor within 15 days of the investigator becoming aware of the event.

Follow up of participants who have experienced a related and unexpected SAE should continue until recovery is complete or the condition has stabilised. Reports for related and unexpected SAEs should be unblinded prior to submission if required by national requirements.

**(vi) Annual reporting of Serious Adverse Events**

Annual Progress reports will be submitted to the Sponsor and the Ethics Committee in accordance with local requirements. The Annual Progress Report will detail all SAEs recorded.

**6.6 Reporting urgent safety measures**

If any urgent safety measures are taken the CI/Sponsor shall immediately and in any event no later than 3 days from the date the measures are taken, give written notice to the relevant REC of the measures taken and the circumstances giving rise to those measures.

**7. STATISTICAL ANALYSES****7.1 Sample Size and power considerations**

Event rate. We used a conservative 27.5% rate of death or unplanned Heart Failure acute care at four years. For context, BLOCK HF saw 39% in the RV pacing mild/moderate LV impairment group, and Abdelrahman et al saw 36% rate in the patients with significant RV pacing.

Effect Size detectable. We plan to be able to detect a 19% relative risk reduction, which is an effect size which would change clinical practice. For context, Biventricular pacing in the BLOCK HF trial delivered a relative risk reduction of 27%. Observational data comparing conduction system pacing with RV pacing shows a 35% lower rate in the physiological pacing group.

Assuming 3.5 years recruitment and 3 years follow up, a conservative survival probability at 4 years of 0.725 (event rate of 27.5%) in the control group and a Hazard Ratio of 0.78 (relative risk of 0.81), 2048 patients would give 85% power with a two-sided  $\alpha$  level of 0.05.

Adjusting for a slower recruitment rate in the first 12 months, a 7.5% cross over from physiological pacing to RV pacing and 7% drop-out, we would need 2539.

## 7.2 Planned recruitment rate

We will recruit 2600, as a total across both UK and international centres. We expect sites to recruit approximately 2.5 patients per month once activated.

Planned recruitment timelines are as below:

*0 to 24 months: Vanguard recruitment:*

*0 to 6 months:* ≥ 12 sites active,

*6 to 12 months:* ≥ 24 sites active,

*12 to 24 months:* 36 sites active.

Expected 1296 patients recruited by 24 months

24 to 42 month: **Main recruitment phase:** 36 sites. Reach 2600 patients.

42 to 78 month: **Follow up phase:** Follow-up will range from 36 to 78 months

